3.4 ON STUDY EVALUATION

3.4.1 Guidelines for Clinical and Laboratory Evaluation

- 3.4.1.1 A complete history and physical examination including signs and symptoms shall be done within 1 month of enrolling on trial.
- 3.4.1.2 Laboratory studies will include a complete blood count (hemoglobin and hematocrit values, white blood cell count, platelet count), BUN, Creatinine, ALT, AST, Total bilirubin, and serum PSA.
- 3.4.1.3 Immunologic studies will include ELISPOT assay, CD3, CD4, CD8 subsets and CD4:CD8 ratio, Class II immune responses, CTL assay, TBNK and sera antibody analyses. The ELISPOT assay is relatively sensitive and quantitative. By measuring cytokine release on a single-cell basis, the assay can detect a peptide-specific T-cell response against specific HLA class I binding peptides. (38) The level of cytotoxicity determined by the standard chromium release assay after *in vitro* expansion of specific T cells has been shown to correlate with the number of γ -IFN releasing cells measured by the ELISPOT assay in a study of both healthy donors and melanoma patients. We have

shown that the ELISPOT assay can be used without prolonged *ex vivo* manipulation of a patient's PBMC to measure immunologic responses in patients receiving cancer vaccines.

3.4.1.4 Testing Schedule (see [Appendix D](#) for tube requirements).

Baseline (Week 1)

See Section [2.4](#)

At time of monthly booster:

History and Physical Exam

Laboratory Evaluation

Research Immunologic Testing

Preop:

History and Physical Exam

PT/PTT/INR

EKG

Laboratory Evaluation

Research Immunologic Testing

Research MRI (if logistically feasible)

---- Surgery ----

NOTES:

* Patients will be monitored for non-laboratory value-based toxicity each visit.

* Inquiries regarding concurrent therapies will be made at each visit.

3.5 STUDY CALENDAR/LABORATORY EVALUATION

	Screening ¹	Baseline ¹	Week 1	Weeks ⁷ 3/5, 5/9, 9/13 (± 1 week)	Week 10 ⁷ (+ 3 months)		Post-Surgery Follow-up ⁴
					Pre-op	Surgery	
History and Physical	X	X	X ⁶	X	X		X
Height	X						
Weight	X			X	X		
Performance Status	X						
HLA class 1 profile		X					
PT/PTT/INR					X		
EKG	X				X		
MRI prostate ²		X			X		
Serum PSA (tumor marker)		X	X ⁶	X	X		X
Pathology confirmation of diagnosis	X						
Immunology Assays ³			X	X	X		X
Lymphocyte Phenotyping (TBNK)			X	X	X		X
Serum HIV antibody	X						
Serum Hepatitis panel	X						
CBC	X	X	X ⁶	X	X		
Acute Care Panel	X						
Hepatic Panel	X						
BUN, Creatinine, ALT, AST, Total bilirubin		X	X ⁶	X	X		
Priming Vaccination			X				
Booster Vaccination				X			
Prostate Biopsy ⁵		X					
Radical Prostatectomy						X	

¹ Please see sections 2.2 and 2.4 for screening and baseline studies respectively.

² MRI of the prostate is strongly encouraged and will be performed prior to and after vaccination course if logistically feasible. Baseline MRI can be obtained within one year prior to treatment.

³ Immunologic assays include ELISPOT assay, CD3, 4, 8 subsets and CD4:CD8 ratio, Class II immune responses, CTL assay, TBNK and sera antibody analysis. Research blood will be drawn prior to each vaccination and then prior to operation.

⁴ Please see section 3.8 for further information on follow up evaluations occurring at 3- 6 months post op and 12 – 15 months post op, and if necessary, the safety visit occurring 4 – 5 weeks after removal from protocol therapy.

⁵ For patients with no evaluable prostate tissue available at time of study enrollment.

⁶ Need not be repeated if they have been performed within the appropriate time frame.

⁷ Patients who were enrolled prior to Amendment B will continue to follow the original week 5, 9 and 13 dosing schedule. However, surgery on these patients can be performed 7-14 days after the last vaccine is given.

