1 INTRODUCTION

1.1 STUDY OBJECTIVES

1.1.1 *Primary*

- The primary objective is to evaluate immunologic CD4 and CD8 cell infiltrate response of a neoadjuvant prime/boost vaccine strategy in prostatectomy specimens: priming with subcutaneous rVaccinia-PSA(L155)-TRICOM (rV-PSA-(L155)-TRICOM) with subsequent monthly boosts using subcutaneous rFowlpox-PSA(L155)-TRICOM (rF-PSA(L155)-TRICOM) in patients planning to undergo radical prostatectomy.

1.1.2 *Secondary*

- To determine the change in peripheral PSA-specific T cells in patients treated with these vaccines.
- To document any intraprostatic T_{reg} cell infiltration with CD4+FOX-P3 staining.
- To document any PSA changes secondary to vaccination, including rate of biochemical recurrence after prostatectomy.
- To document any MRI changes secondary to vaccination

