Neoadjuvant use of a prostate cancer vaccine makes sense because the patient has a low volume of disease (organ confined) and has an intact immune system (surgical patients are younger, healthier, and have not been exposed to systemic therapies or have occult bone marrow metastasis as is often seen in men with metastatic castration-resistant prostate cancer who receive vaccine therapy after progressing on chemotherapy). Although no data currently exist with neoadjuvant vaccine in localized prostate cancer, outcomes with patients with lower metastatic burden have demonstrated a greater prolonged effect of delaying disease onset and progression. The patient population in this study has very low tumor burden only locally present and thus is the earliest patient population that could be treated. The potential benefits are a prolonged action of the prostate vaccine on preventing growth of any micrometastatic disease that may be present. This risk may be quite low in the low risk subgroups however is not zero in any patient. The vaccine has been demonstrated to be safe in multiple trials and thus even in the setting of uncertain benefit, this is a therapy that poses minimal risk to the patient population enrolled in the trial. A topic of interest within this study will be to examine if neoadjuvant use demonstrates similar activation of T-cell immunity as compared to use at time of metastatic disease. CD4 and CD8 cell infiltrates were chosen as primary outcome measures as they represent the immune mechanism by which the vaccine ultimately has effect and have been used in recent trials with success (32). Previous studies (29) have already demonstrated a strong correlation between T-cell infiltrate and overall vaccine efficacy for overall survival.

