2 ELIGIBILITY ASSESSMENT AND ENROLLMENT

2.1 ELIGIBILITY CRITERIA

2.1.1 Inclusion Criteria

- 2.1.1.1** Patients must have histopathological documentation of adenocarcinoma of the prostate prior to starting this study and evaluable biopsy tissue (e.g., unstained slides or blocks) available for analysis. If evaluable tissue is not available, the patient must agree to undergo a pre-vaccination prostate biopsy on study as an alternative to having available tissue available.
- 2.1.1.2** Patients must be a surgical candidate for radical prostatectomy based on standard workup of PSA, biopsy results, and if necessary supplemental imaging.
- 2.1.1.3** Patients must have chosen radical prostatectomy as their definitive treatment of choice for management of their prostate cancer.
- 2.1.1.4** Patients must have a performance status of 0 to 1 according to the ECOG criteria (see [Appendix A](#)).
- 2.1.1.5** No systemic steroid or steroid eye drop use within 2 weeks prior to initiation of experimental therapy. Limited doses of systemic steroids to prevent IV contrast, allergic reaction or anaphylaxis (in patients who have known contrast allergies) are allowed.
- 2.1.1.6** Hematological eligibility parameters (within one month of starting therapy):
 - Granulocyte count $\geq 1,500/\text{mm}^3$
 - Platelet count $\geq 50,000/\text{mm}^3$
 - Hgb ≥ 8 g/dL

- 2.1.1.7** Biochemical eligibility parameters (within one month of starting therapy):
- a. Hepatic function: Bilirubin < 1.5 mg/dl (OR in patients with Gilbert's syndrome, a total bilirubin \leq 3.0 mg/dL), AST and ALT < 2.5 times upper limit of normal.
 - b. Creatinine \leq 1.5 X ULN
 - c. Patients must be test negative for HIV, Hepatitis B and C.
- 2.1.1.8** Patients must not have other active invasive malignancies within the past 2 years (with the exception of non-melanoma skin cancers) or life threatening illnesses.
- 2.1.1.9** Patients must be willing to travel to the study site for follow-up visits.
- 2.1.1.10** Patients must be \geq 18 years of age.
- 2.1.1.11** All patients who have received prior vaccination with vaccinia virus (for smallpox immunization) must not have a history of allergy to the vaccine.
- 2.1.1.12** Patients must understand and sign informed consent that explains the neoplastic nature of their disease, the procedures to be followed, the experimental nature of the treatment, alternative treatments, potential risks and toxicities, and the voluntary nature of participation.

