2.4 BASELINE STUDIES (WITHIN 4 MONTHS PRIOR TO TREATMENT)

Baseline examinations need not be repeated if they have been performed within the appropriate time frame.

- History and Physical Exam
- HLA class 1 profile
- Serum PSA (tumor marker)

- CBC
- BUN, Creatinine
- ALT, AST, Total bilirubin
- Lymphocyte Phenotyping (TBNK)
- Research Studies (See section 5 for details)
 - MRI prostate¹ (can be obtained within one year prior to treatment)
 - Immunology assays (including immune T-cell response assay, CD3, 4, 8 subsets and CD4:CD8 ratio, Class II immune responses, CTL assay, TBNK, and sera antibody analyses)
 - Prostate biopsy (performed only if previously collected tissue is not available. If biopsy was performed at screening, leftover material may be used for research study.)

¹ MRI of the prostate is strongly encouraged and will be performed prior to and after vaccination course if logistically feasible.

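### The Week 1 PSA can be waived, so the PSA baseline may precede the first vaccine by up to about 17 weeks; the MRI and archived-biopsy baselines may be older still

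*Combined protocol and SAP*

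**What the plan says.** **PSA.** Section 2.4 lists serum PSA among baseline studies that may be done up to 4 months before treatment. In Section 3.5 the PSA row is marked at both Baseline and Week 1, and the Week 1 mark carries footnote 6: "Need not be repeated if they have been performed within the appropriate time frame". A secondary objective (Section 1.1.2) is "To document any PSA changes secondary to vaccination, including rate of biochemical recurrence after prostatectomy".

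**MRI.** Footnote 2 of Section 3.5 states "Baseline MRI can be obtained within one year prior to treatment", and Section 2.4 says the same. MRI change is also a secondary objective.

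**Biopsy.** Inclusion criterion 2.1.1.1 asks for "evaluable biopsy tissue (e.g., unstained slides or blocks) available for analysis" and sets no maximum age. Under Section 2.4 a new biopsy is taken only when no earlier tissue can be had. This tissue is the baseline for the primary CD4 and CD8 fold changes (Section 8).

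**Other therapy.** Section 4.1 bars concurrent anti-tumor therapy, and Section 3.4.1.4 asks about concurrent therapies at each visit. The background (Section 1.2.1) describes surgical patients as men who "have not been exposed to systemic therapies". Section 2.1 contains no matching criterion, and no section requires therapy between biopsy and first vaccine to be recorded.

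**Analysis.** Section 8 defines no PSA or MRI baseline and no analysis that takes account of baseline age.

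**The concern.** With no control arm, each before/after comparison relies on its baseline to show what would have happened without vaccine. Time between that baseline and the priming dose adds untreated change to the estimate. For PSA this is avoidable: the patient attends at Week 1 and gives research blood that day, yet the draw that would fix the pre-vaccine level is optional. A man whose only pre-vaccine PSA is four months old contributes a difference that mixes four months of natural course with the vaccination period.

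The same reasoning applies to a year-old MRI, and to archived tissue of any age. For the tissue, the plan also has no means of identifying a man who received prostate cancer therapy after the biopsy and stopped before enrolment.

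**Working it through.** **The plan's own figure.** Section 8: 24 patients, effect 0.67 SD of the change, two-sided 0.025 paired t-test, 80% power. Noncentral t with 23 df and noncentrality 0.67 × √24 = 3.28 gives 80.5%, so the stated figure reproduces. The sample size is not in question.

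**Inputs.**
- 1 month = 365.25/12/7 = 4.35 weeks. The PSA limit of 4 months is 17.4 weeks and the MRI limit of 1 year is 52.2 weeks (Sections 2.4, 3.5).
- Prime at week 1 to surgery at week 10: 9 weeks (Section 3.1). With the 3-month allowance: 9 + 13.0 = 22.0 weeks.
- Patients enrolled before Amendment B: last booster at week 13, surgery 7–14 days later, so 13–14 weeks. With 14 days plus 3 months: 14 + 13.0 = 27.0 weeks (Sections 3.1, 3.6).
- The précis gives 4 months of treatment before surgery, or 17.4 weeks. This differs from the week 10 schedule, and the two must be reconciled.

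**Formula.** Unvaccinated share = lead time / (lead time + time from prime to surgery), with the baseline at its permitted limit.

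| Time from prime to surgery | PSA, 17.4 weeks | MRI, 52.2 weeks |
|---|---|---|
| 9 weeks | 17.4/26.4 = 66% | 52.2/61.2 = 85% |
| 13–14 weeks (before Amendment B) | 57–55% | 80–79% |
| 17.4 weeks (précis) | 50% | 75% |
| 22.0 weeks (full delay) | 44% | 70% |
| 27.0 weeks (before Amendment B, full delay) | 39% | 66% |

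Section 3.6 gives the allowance as 12 weeks. On that reading the third-longest interval, 21 weeks, gives 45% for PSA and 71% for MRI.

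**Inside the limit.** A PSA taken 2 months (8.7 weeks) before the prime, with surgery at week 10, gives 8.7/17.7 = 49%.

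**PSA drift (assumption).** The documents give no PSA doubling time. If it were 1 year, drift over the lead time would be 2^(17.4/52) − 1 = 26%; if 3 years, 2^(17.4/156) − 1 = 8%.

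**Biopsy (assumption).** No age limit is stated. Assumed ages of 6, 12 and 24 months give shares of 74%, 85% and 92% with surgery at week 10, and 54%, 70% and 83% with the full delay. The documents do not say whether infiltrate drifts over such periods. As a sensitivity calculation only: non-vaccine drift of 0.2, 0.3 or 0.5 SD of the change would make the 24-patient test significant 9.5%, 20% or 53% of the time with no vaccine effect, against a nominal 2.5%.

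**Peripheral immunology blood.** Its Week 1 mark in Section 3.5 carries no footnote 6, and footnote 3 has research blood drawn before every vaccination. That baseline sits at the first dose.

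**The case against.** Several counter-arguments are sound. The default calendar does contain a Week 1 PSA, and footnote 6 only permits an exemption. PSA is repeated at each booster visit and before surgery, so a trend on vaccine can be seen; Section 1.2.2.6 expects a slower PSA rise rather than a fall, which makes serial values informative. The PSA and MRI objectives are descriptive, MRI depends on logistics, and Section 8 tests neither. Accepting diagnostic tissue is a deliberate choice that spares men a second biopsy. A share of calendar time is also not a share of the measured change.

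These points limit the size of the problem but do not remove it. The later PSA values all follow the prime and cannot supply a pre-vaccine level.

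Three stronger readings should be resisted:
- A reader might infer that the measured changes consist mostly of unvaccinated time. That holds only near the permitted limits. For PSA it fails when surgery is fully delayed, and already at a 2-month-old value with surgery at week 10.
- A reader might infer that other therapy contaminates the primary endpoint. No document says that any patient received therapy between biopsy and first vaccine; the gap is that the plan neither excludes nor records it.
- A reader might infer that all baselines are affected. The peripheral T-cell baseline is not.

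**Conclusion.** The point holds as a gap in how baselines are secured. No PSA close to the first vaccine is guaranteed, although an objective attributes PSA change to vaccination. At the permitted limit the unvaccinated share is 66% for PSA with surgery at week 10 (39–44% with the full 3-month delay) and 85% for MRI (66–70%). These shares rest on the stated windows and are worst cases; the documents give no distribution of actual lead times. For the archived biopsy, the finding is the missing age limit and the missing record of interval therapy. It matters because this tissue anchors the primary endpoint, but any bias in CD4 or CD8 fold change is unquantified, and the drift figures above are assumptions. The planned sample size and power stand.

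**What to change.** 1. **PSA.** Remove footnote 6 from the serum PSA row of Section 3.5, so that a Week 1 PSA drawn before the priming vaccine is mandatory, and name it in Section 8 as the PSA analysis baseline. Add a line in Section 2.4 so that its general waiver of repeat examinations does not override this. Cost: one 4 mL tube per patient (Appendix D) at a visit where research blood is already drawn.
2. **Records.** Capture the dates of the baseline MRI and baseline biopsy, and any prostate cancer therapy between biopsy and first vaccine. Cost: a few data fields.
3. **Primary endpoint.** Keep all evaluable patients in the primary analysis. Prespecify two sensitivity analyses: one excluding patients with interval therapy, and one excluding patients whose biopsy is older than a cut-off fixed before analysis, for example the 4-month window of Section 2.4. Dropping patients from the primary analysis instead would use up a margin of only three (27 enrolled for 24 evaluable); at the planned effect, 22 patients give 76% power and 21 give 74%. The sensitivity analyses will have less power and should be read for consistency of the estimate.
4. **MRI.** Report change separately for baselines inside and outside 4 months. The cost is smaller groups in a descriptive analysis.

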3.6 SURGICAL GUIDELINES

Patients will undergo a radical prostatectomy after week 10 of the study. The radical prostatectomy may be performed any day after week 10 or up to 12 weeks after to allow for logistical constraints, but ideally as close to week 10 as possible. Patients enrolled prior to amendment B will have their surgery within 7 to 14 days after the last dose of vaccine plus 3 months to allow for logistical constraints. The surgery performed will typically be a robotic-assisted laparoscopic radical prostatectomy with bilateral pelvic lymph node dissection according to standard surgical template, however this may vary significantly depending on the clinical scenario and judgment of the surgeon. Although strongly encouraged, a lymph node dissection may be excluded if felt to be in the best interest of the patient. Alternative approaches may also be utilized to perform the radical prostatectomy as felt appropriate by the surgeon. Acquired tissue will be analyzed by pathology per their usual protocol to provide a diagnosis and appropriate grade and staging information regarding the patient's cancer. In addition, additional slides will be kept for research analysis by immunohistochemistry as well as material may also be procured and frozen for future molecular based analysis (See section 5.1 for further details).

Patients undergo preparation that is standard of care for radical prostatectomy. The surgery will be performed per routine by the surgeon.

3.7 CRITERIA FOR REMOVAL FROM PROTOCOL THERAPY AND OFF STUDY CRITERIA

Prior to removal from study, effort must be made to have all subjects complete a safety visit approximately 30 days following the last dose of study therapy.

3.7.1 *Criteria for removal from protocol therapy*

Patients will be removed from the protocol therapy for the following:

1. Grade 3 or greater toxicity attributed to vaccines that does not resolve to grade 1 within 42 days from time of scheduled treatment.
2. Grade 2 or greater autoimmune disease that threatens vital organs.
3. Intercurrent illness or medical circumstances. If at any time the constraints of this protocol are detrimental to the patient's health, the patient may be removed from protocol therapy and reasons for withdrawal will be documented.
4. Greater than 3 month delay in the performance of radical prostatectomy from week 10 or date that patient first becomes eligible for surgery.

3.7.2 *Off-Study Criteria*

Patients will be removed from the study for the following:

1. Patient has completed all study interventions including follow up safety visit
2. Patient requests to be taken off study. Reasons for withdrawal will be documented.
3. Noncompliance with protocol guidelines (patient removed at discretion of Principal Investigator).
4. Death

3.7.3 Off Protocol Therapy and Off Study Procedure

Authorized staff must notify Central Registration Office (CRO) when a subject is taken off protocol therapy and when a subject is taken off-study. A Participant Status Updates Form from the web site (<http://home.ccr.cancer.gov/intra/eligibility/welcome.htm>) main page must be completed and sent via encrypted email to: NCI Central Registration Office (HOIS) [contact].

3.8 FOLLOW-UP EVALUATION

Subjects will be seen 3 – 6 months post operatively as well as 12 – 15 months postoperatively. The following assessments will be performed at these visits:

- History and Physical Exam
- PSA
- ELISPOT assay, CD3, CD4, CD8 subsets and CD4:CD8 ratio, Class II immune responses, CTL assay.

If subjects have stopped taking the study vaccination for any of the reasons listed in section **3.7.1** prior to prostatectomy, they will be seen at NIH, if feasible, for a safety visit within 4-5 weeks of last vaccination. The safety assessments may be performed by a local physician and laboratory if patients unable to return to the NIH Clinical Center at this time.

The following assessments will be performed at the safety follow up.

- History and Physical Exam
- Laboratory Evaluation (CBC, BUN, Creatinine, ALT, AST, Total bilirubin, and serum PSA).

After the safety visit, if there are no unresolved grade 3 or higher AEs, the patient will not require further safety follow-up. If there are unresolved grade 3 – 4 AEs, patients will be followed either at the NIH clinical center or by their local physician until symptoms stabilize. In the latter case, we will obtain the physician's record of AEs.

4 CONCOMITANT MEDICATIONS/MEASURES

4.1 CONCURRENT THERAPIES

Concurrent anti-tumor therapies will not be allowed.

4.2 SUPPORTIVE CARE

1. For the vaccine administration, antiemetics and anti-diarrheal agents may be administered as required, but are not anticipated to be needed and should not be used prophylactically on the first cycle. The selection of the specific antiemetic regimen is at the discretion of the treating physician. Patients on this protocol should avoid being given dexamethasone or other corticosteroids (with the exception of topical and inhaled steroids) particularly in the two-week period post vaccinia treatment. If their medical condition requires this therapy, the principal investigator must be notified.

2. Other supportive care with blood components, antibiotics, analgesics, general medical therapy, etc., will be delivered as required. Any patients taking antibiotics for any reason must complete that course of therapy and be free of evidence of further infection for 3 days before receiving any dose of vaccine.
3. Symptomatic anemia should be treated with appropriate red blood cell or erythropoietin support.
4. Thrombocytopenia should be treated conservatively. In the absence of bleeding or a planned invasive procedure, platelet transfusions should be given for a platelet count below 10,000/mm³. If invasive procedures are planned or the patient develops bleeding, platelet transfusions should be administered in accordance with the standard of practice, usually maintaining a platelet count of >50,000/mm³.
5. Nutritional support and psychosocial support. During cancer treatments it is sometimes difficult for patients to maintain good nutrition. If it is deemed necessary, or it could benefit the patient, the patient will be referred for a nutritional consult. Patients who are having emotional difficulty coping with their disease and/or their treatment will be referred to a social worker for evaluation and support.
6. Early institution of VIG therapy is advised following recognition of clinical symptoms compatible with some vaccinia complications (eczema vaccinatum, severe generalized vaccinia, progressive vaccinia, and some cases of autoinoculation). The effectiveness of VIG therapy appears to be time-dependent. VIG is of no benefit in the treatment of postvaccinial encephalitis, and is contraindicated for treatment of vaccinial keratitis. At present there is no other available anti-viral treatment of proven benefit for vaccinia-related complications. VIG is an isotonic sterile solution of the immunoglobulin fraction (antibodies) of plasma from persons vaccinated with vaccinia vaccine. If symptoms develop suggestive of the acquisition of one of the previously described vaccinia complications, or a close contact occurs between a recently vaccinia-vaccinated patient and a susceptible person with one of the pre-existing medical conditions described above, the patient should report the findings immediately to the protocol investigator or other established contact, for consideration for VIG therapy.
7. Any evidence of disseminated intravascular coagulation (DIC), hemolytic uremic syndrome (HUS), or thrombotic thrombocytopenic purpura (TTP) including thrombocytopenia, hemolytic anemia, renal failure, fever or neurologic changes should be thoroughly evaluated and closely monitored and supported as clinically indicated.

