3. **Inadvertent Inoculation:** This can occur in the vaccinee (autoinoculation) as well as in close contacts (contact transmission). Accidental infection is the most common complication of vaccinia vaccination, accounting for approximately 50% of all complications associated with vaccination and revaccination. This usually results from autoinoculation of vaccinia virus transferred from the site of the vaccination. Sites typically involved include the face, eyelids, nose, mouth, genitalia, or rectum, but can also involve the arms, legs, and trunk. Contact transmission of vaccinia, with accompanying toxicities, may occur when a recently vaccinated individual has contact with a susceptible individual. In a 1968 ten-state survey, contact transmissions were reported to occur at a rate of 27 infections per million vaccinations. The age group in which contact transmission occurred most commonly was in children ≤ 5 years. Eczema vaccinatum as a result of contact transmission may result in a more severe syndrome than that seen in vaccinees, perhaps because of multiple simultaneous inoculations. About 30% of eczema vaccinatum cases reported in the 1968 ten-state survey were a result of contact transmission. It is possible that the number of cases of contact transmission would be greater in today's population, due to a largely unvaccinated patient population against smallpox. Contact transmission rarely results in postvaccinial encephalitis or progressive vaccinia. Most cases of inadvertent inoculation usually resolve without specific therapy and resolution of lesions

follow the same course as the vaccination site in immunocompetent individuals. VIG can be used for severe cases involving extensive lesions or if comorbid conditions exist. VIG is contraindicated in the presence of isolated keratitis due to the risk of increased corneal scarring. VIG use can be considered in cases of ocular implantation, with keratitis, if vision-threatening or if other life-threatening vaccinia-related complications exist that require VIG therapy.

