11.2.12 Treatment of Vaccinia Vaccination Complications

Vaccinia Immune Globulin (VIG): First-line treatment of some of the complications of vaccinia caused by dissemination of vaccinia virus (severe cases of inadvertent inoculation involving extensive lesions or if comorbid conditions exist, severe cases of generalized vaccinia in patients that are systemically ill and whose condition might be toxic or who have serious underlying immunosuppressive illnesses, eczema vaccinatum, and progressive vaccinia) is with VIG. VIG is contraindicated, however, for the treatment of isolated vaccinia keratitis. VIG is a sterile solution of the immunoglobulin fraction of pooled plasma from individuals inoculated with vaccinia vaccine. VIG is only available through the CDC's Strategic National Pharmaceutical Stockpile by contacting the CDC's Clinician Information Line at [name] or the Director's Emergency Operations Center (DEOC) at [contact]. Upon receipt of a call from a patient or upon direct observation of a patient or contact who manifests signs and symptoms of any of the above conditions, the investigator should place a call to the CDC as soon as possible: 1) to initiate review of the clinical case, 2) to seek consultation on the appropriateness of VIG therapy, 3) to determine the appropriate VIG dose and dosing method for administration, if VIG therapy is required, and 4) to determine how to access and have the appropriate doses of VIG delivered. Early institution of

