VIG therapy is advised following recognition of clinical symptoms compatible with some vaccinia complications (eczema vaccinatum, severe generalized vaccinia, progressive vaccinia, and some cases of inadvertent inoculation). The effectiveness of VIG therapy appears to be time dependent. VIG has not proven to be of benefit in the treatment of post-vaccinial encephalitis, and is contraindicated for treatment of isolated vaccinial keratitis due to the increased risk of corneal scarring. A new IV formulation of VIG that has a lower level of aggregated protein allowing it to be used by either the IM or IV route is available through the CDC. This formulation will most likely be preferred for administration and the CDC will instruct investigators regarding appropriate dosing and method of administration based on the formulation and availability. There is no guarantee that VIG will successfully treat complications. At present, there are no other anti-viral therapies of proven benefit for the treatment of vaccinia-related complications.

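### Section 4.2 item 6 rules out VIG for all vaccinial keratitis, while sections 11.2.11 and 11.2.12 rule it out only for isolated keratitis; the VIG source and dose lines in 10.4.4 also do not match 11.2.12

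*Combined protocol and SAP*

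**What the plan says.** **Section 4.2, item 6 (supportive care).** VIG "is contraindicated for treatment of vaccinial keratitis". The same item advises early VIG for several complications, including "some cases of autoinoculation", says its effectiveness appears to depend on timing, and has patients with suggestive symptoms report at once "for consideration for VIG therapy". It does not point to section 11.

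**Section 11.2.11, item 3 (inadvertent inoculation).** "VIG is contraindicated in the presence of isolated keratitis due to the risk of increased corneal scarring". It goes on: "VIG use can be considered in cases of ocular implantation, with keratitis, if vision-threatening", "or if other life-threatening vaccinia-related complications exist that require VIG therapy".

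**Section 11.2.12 (treatment of complications).** The limit appears twice: "VIG is contraindicated, however, for the treatment of isolated vaccinia keratitis", and later VIG "is contraindicated for treatment of isolated vaccinial keratitis due to the increased risk of corneal scarring". This section also gives the CDC stockpile as the only route to VIG. It tells the investigator to call the CDC about appropriateness, dose, method and delivery. It expects a newer product usable IM or IV to be preferred, with the CDC instructing on dose and method by formulation and availability.

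**Section 10.4.4 (risk-benefit).** A sentence on the CDC's VIG supply excepts vaccinia keratitis, again unqualified. The bullets beneath it list the CDC Drug Service and the U.S. Army as sources and give a dose of 0.6 ml/kg IM, with no product strength or formulation.

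**The concern.** Section 4.2 is the supportive-care text, and a treating physician may read item 6 without turning to the pharmaceutical section. The patient at issue has ocular implantation of vaccinia with keratitis that threatens sight. Read literally, item 6 closes off a treatment that 11.2.11 item 3 leaves open. The protocol itself treats this as a serious outcome: 11.2.11 item 3 names the eyelids among typical sites of accidental infection, and the vaccinia toxicity scale in 6.3.2 uses blindness as its example of Grade 4 autoinoculation with sequelae. Since 4.2 item 6 also calls VIG time-dependent, a delay while conflicting text is reconciled could matter.

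The 10.4.4 bullets raise a smaller practical question. Someone acting on them could approach a source that 11.2.12 does not recognise, or draw up a volume-based dose without knowing which product it was meant for.

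**Working it through.** No sample size, power or event figure is involved, so the check is a side-by-side reading of the current text.

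**Keratitis rule**

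| Place | Form of statement | Limited to isolated keratitis? | Vision-threatening exception? |
|---|---|---|---|
| 4.2 item 6 | contraindication | no | no |
| 10.4.4 | exception within a supply sentence | no | no |
| 11.2.11 item 3 | contraindication | yes | yes |
| 11.2.12, first statement | contraindication | yes | not repeated |
| 11.2.12, second statement | contraindication | yes | not repeated |

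Keratitis is therefore unqualified in two places and qualified in three. Of the two, only 4.2 item 6 is an actual contraindication.

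Applied to three kinds of patient:

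1. *Isolated keratitis.* Every section says not to use VIG. No conflict.
2. *Ocular implantation with vision-threatening keratitis.* Section 4.2 item 6 says contraindicated; 11.2.11 item 3 says VIG can be considered. This is a direct conflict.
3. *Keratitis together with another life-threatening complication that itself needs VIG.* Section 11.2.11 item 3 allows VIG. Section 4.2 item 6 bars it as treatment of keratitis, but here it is given for the other complication, and the same item advises early VIG for eczema vaccinatum, progressive vaccinia and severe generalized vaccinia. No clear conflict.

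The conflict is confined to the second patient.

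**Source.** Section 10.4.4 lists two suppliers, one of them the U.S. Army. Section 11.2.12 gives the CDC stockpile as the sole route. Both cannot be right.

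**Dose and route.** Section 10.4.4 fixes 0.6 ml/kg IM. Section 11.2.12 gives no number and defers to the CDC by formulation. The mismatch is a fixed dose against case-by-case instruction. Without a product strength, the ml/kg figure cannot be checked or carried over to another formulation.

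**Frequency.** The documents state no rate for keratitis. Section 10.4.4 quotes overall vaccinia complication rates of 0.0108% with prior vaccination and 0.1253% without. These cover all complications and cannot be turned into a keratitis count for the 27 patients.

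**The case against.** The strongest reply is that no treatment decision turns on these words. Section 4.2 item 6 routes symptomatic patients to consideration of VIG and favours early use in some autoinoculation. Section 11.2.12 has the investigator call the CDC as soon as possible about appropriateness, dose and access, and on its account VIG cannot be obtained any other way. Section 10.4.4 is risk-benefit background, IM remains a valid route for the newer product, and the preference for that product is a forecast. All of this stands, and it makes harm unlikely. It does not make the texts agree: a physician who takes item 6 at its word could rule VIG out before calling, and item 6 has no pointer to correct that.

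A reader might infer three stronger points that the documents do not support.

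- *That 10.4.4 directs VIG for every kind of complication except keratitis, against the section 11 statements that it is not indicated for rashes and not recommended for CNS disease.* The 10.4.4 sentence describes a supply that the CDC holds; it is not an indication. Counting rows of the 10.4.4 complication table for which VIG is unsuitable does not help either, since the count depends on how rows such as the catch-all category are classified.
- *That both parts of the 11.2.11 exception conflict with 4.2.* Only the vision-threatening part clearly does, for the reason given for the third patient above.
- *That the protocol prints two different VIG doses.* Section 11 has no competing figure.

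**Conclusion.** The point holds as a minor inconsistency in safety text that is wrong as written. On the keratitis rule, 4.2 item 6 is broader than the three statements in 11.2.11 and 11.2.12, and for vision-threatening ocular implantation it contradicts 11.2.11 item 3. The unqualified wording in 10.4.4 shares the omission. On source, 10.4.4 and 11.2.12 contradict each other outright. On dose, 10.4.4 states a fixed figure where 11.2.12 leaves the matter to the CDC.

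The conclusion rests on the plain reading of the current text and assumes that section 11, the more detailed and internally consistent account, reflects the intended rule. The consequence is small: the event is expected to be rare, although the documents do not quantify it, and the CDC call is an effective safeguard. The endpoint, eligibility, sample size, visits and analysis are unaffected.

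**What to change.** **Section 4.2, item 6.** Change the wording to *isolated vaccinial keratitis*, and add a cross-reference to the exception in 11.2.11 item 3 and to the CDC call in 11.2.12. The reference to 11.2.11 is needed because 11.2.12 does not repeat the ocular exception.

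**Section 10.4.4.** Qualify keratitis as *isolated*, and replace the VIG source and dose bullets with a cross-reference to 11.2.12, so that the protocol carries one set of VIG instructions.

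The cost is protocol wording in two sections, with no effect on enrolment, visits or analysis.
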